#### **Secondary Efficacy Endpoints**

- Change in systolic blood pressure (SBP) from baseline (Screening Visit 2) as measured by 24-hour Ambulatory Blood Pressure Monitoring (ABPM) at 3, 6, 12, 24 and 36 months post-procedure.
- Change in office systolic blood pressure from baseline (Screening Visit 2) at 1, 3, 6, 12, 24 and 36 months post-procedure.
- Incidence of achieving target office systolic blood pressure (SBP <140 mmHg) at 1, 3, 6, 12, 24 and 36 months post-procedure.
- Change in office diastolic blood pressure from baseline (Screening Visit 2) at 1, 3, 6, 12, 24 and 36 months post-procedure.
- Change in diastolic blood pressure from baseline (Screening Visit 2) as measured by 24-hour Ambulatory Blood Pressure Monitoring (ABPM) at 3, 6, 12, 24 and 36 months post-procedure.

Summary of Quality of Life (QOL) Measures (EQ5D and SF36)

## 5.3. Additional analyses

The following additional analyses will be conducted:

- Antihypertensive medication usage throughout the study, including escape subjects prior to 3-months and subjects reintroduced to medications after 3 months.
- Additional procedural characteristics e.g. treatment duration, frequency of distal renal artery treatment, ablations per vessel, location of ablations, number of ablations per patient and other characteristics will be analyzed to assess their impact on blood pressure.

# 6. Investigation Plan

The SPYRAL PIVOTAL – SPYRAL HTN-OFF MED study is a multi-center, international, prospective, single blinded, randomized, interventional, sham-controlled study. In order to demonstrate that catheter-based renal denervation using the Symplicity Spyral catheter and the Symplicity G3 generator is an effective and safe treatment for hypertension in the absence of antihypertensive medications, study subjects will be randomized to the Denervation or Control group in a 1:1 fashion. Subjects will be studied in the absence of antihypertensive medications to assess the impact of renal denervation on systolic blood pressure in the absence of medication. Patients with hypertension will be enrolled in accordance with the inclusion

and exclusion criteria specified in the protocol. Approximately 1800 subjects will be screened in order to randomize up to 433 subjects, which includes 80 subjects to be used as an informative prior in a Bayesian analysis. Subjects will be enrolled at up to 50 study centers in the United States, Canada, Japan, Australia and countries where CE mark applies. Additional geographies may be added. Enrollment is expected to take approximately 33 months. Subjects may participate in the study from the time of signing consent until completion of three years of follow-up after procedure. Control subjects may be offered renal denervation therapy (crossover) after their 6 month follow-up visit and will be followed-up for two years.

# 7. Randomization and Blinding

Randomization will be stratified by study center at a 1:1 ratio to:

- Denervation group (RDN): Subjects remain blinded and are treated with the renal denervation procedure.
- Control group: Subjects remain blinded and remain on the catheterization lab table for at least 20 minutes prior to introducer sheath removal.

Investigational sites will access randomization allocation via a password-protected system that can only be accessed by those approved by the study sponsor.

All study staff and necessary hospital personnel will be instructed that subjects are not to be informed of their randomization assignments and appropriate measures should be taken to minimize the risk of premature unblinding.

The Investigator performing the catheterization lab procedures and his/her designated study staff will be blinded to a subject's randomization group up until the angiography is completed and inclusion/exclusion confirmed. However, investigators performing study follow-up visits and the subject's referring/managing physicians will not be proactively informed of a subject's treatment assignment to minimize potential bias in the subject's care decisions. However, to specifically minimize potential bias in the measurement of Office BP and ABPM, each investigational site will specify several designated "blinded" members of their study staff that will not be informed of the subject's group assignments and will be responsible for performing the office blood pressure measurements, conducting ABPM preparation and printing results upon a patient completing the ABPM. Prior to unblinding, the blinding effectiveness will be assessed by asking blinded study staff which group they believe the subject was randomized to.

[figure not shown]
Subjects will be blinded during the renal angiogram by a combination of conscious sedation, sensory isolation (e.g., blindfold and music), and lack of familiarity to the procedural details and duration (i.e., subjects will not know the difference between the renal angiography procedure alone and the renal angiography and denervation procedure). Subjects will continue to be blinded by only interacting with blinded site personnel through the 6 month follow-up visit post-procedure. Blinding effectiveness will be assessed by asking the subject which group they believe they were randomized to. All subjects will be unblinded after the completion of their required 6-month follow-up testing.

# 8. Determination of Sample Size

This study will be conducted as an adaptive Bayesian trial with an informative prior. A Bayesian power prior approach [3,4] in conjunction with a discount function will be used to incorporate the prior data. The discount function reduces the strength of the prior data if disagreements are observed with the pivotal data.

The prior data consists of the first consecutively randomized 80 patients in the SPYRAL HTN-OFF MED study, the results from these 80 subjects have been analyzed and published [6]. The weight of the prior data will be adjusted using a discount function, which scales from 0 to 1, according to the similarity of the prior and pivotal data. This discount function adjusts the amount of weight the prior receives. This prevents the use of an informative prior where exchangeability issues are present (e.g., the prior and pivotal data are quite different). This discount function approach was proposed by the Medical Device Innovative Consortium (MDIC) working group and is a collaborative effort between FDA and industry through the MDIC [1,2]. If the analyses show a high level of agreement for pivotal data compared to the prior, the prior will be weighted at or near 100%. If the pivotal data perform worse than or much better than the prior, then the prior will receive very little or zero weight. The Bayesian adaptive design is set up to enroll patients until a sufficient sample size is achieved to have high probability of meeting the endpoint.

The sample size of the study will vary from 210 to 300 subjects with 3-month follow-up due to the adaptive nature of the trial. This will require approximately 247 to 353 randomized subjects to account for a 15% attrition at 3-months. Based on this attrition rate, the interim analyses will take place after the 210th and 240th subjects have completed 3-month follow-up, with a maximum study size of 300 subjects if the study does not stop at either interim look. The actual rate of attrition will dictate the available sample size for analyses. At each interim analysis, enrollment may be stopped for efficacy or futility.

Simulations of trial design operating characteristics performed to demonstrate control of type I error & power are presented in section 9.9.6 for the primary and secondary efficacy endpoints.

### 9. Statistical Methods

## 9.1. Study Subjects

#### 9.1.1. Disposition of Subjects

A subject disposition table will be provided for each follow-up visit containing the following information:

- The number of subjects who died or withdrew prior to each follow-up
- The number of subjects eligible for each follow-up visit
- The number of subjects completing each follow-up visit within the protocol specified window
- The number of subjects completing each follow-up outside the protocol specified window
- The number of subjects who did not complete their follow-up

### 9.1.2. Clinical Investigation Plan (CIP) Deviations

A study deviation is an event where the investigator or investigational site personnel did not conduct the clinical study according to the Clinical Investigation Plan or Clinical Study Agreement. The investigator is not allowed to deviate from the above mentioned documents except with prior approval and under emergency circumstances. All deviations shall be documented and explained, regardless the reason for the deviation. Medtronic will assess the significance of all deviations and evaluate the need to amend the Clinical Investigation Plan or to early terminate the investigation, in accordance with Medtronic SOPs.

#### 9.1.3. Analysis Sets

#### 9.1.3.1. Intention-To-Treat (ITT) Population

This is the primary analysis set for efficacy and safety evaluation and consists of all randomized subjects, analyzed according to their randomized treatment. Subjects who meet the anti-hypertensive medication escape criteria (OSBP>180 mmHg or safety reasons) will be analyzed using Last Observation Carried Forward (LOCF) for their blood pressure measurements out to 3 months. Safety outcomes, and office and ambulatory blood pressure outcomes at each follow-up visit will be presented for this population.

#### 9.1.3.2. Modified Intention-To-Treat (ITT) Population

All randomized subjects, analyzed according to their randomized treatment. Subjects who meet the anti-hypertensive medication escape criteria (OSBP>180 mmHg or safety reasons) will be excluded from this population. Office and ambulatory blood pressure outcomes out to 3 months will be presented for this population.

#### 9.1.3.3. Per Protocol Population

All randomized subjects, meeting the following criteria:

- 1. Subjects showing medication compliance in blood and/or urine (via drug testing data) at screening visit 2 (SV2) and 3-months.
- 2. Exclude subjects with protocol deviation code 101 (consent not obtained).
- 3. Exclude subjects who do not meet the following Inclusion/Exclusion criteria.

- Inclusion: Individual has an office systolic blood pressure (SBP) ≥150 mmHg and <180 mmHg and an office DBP ≥ 90 mmHg measured at Screening Visit 2, according to the guidelines in Appendix L7 of the study protocol.
- Inclusion: Individual has a 24-hour ABPM average SBP ≥140 and <170 mmHg measured at Screening Visit 2, according to guidelines in Appendix L7 of the study protocol.
- Exclusion: Individual has undergone prior renal denervation.
- Exclusion: Individual has renal artery anatomy that is ineligible for treatment.
- Exclusion: Individual has one or more of the following conditions: stable or unstable angina within 3 months of enrollment, myocardial infarction within 3 months of enrollment; heart failure cerebrovascular accident or transient ischemic attack or atrial fibrillation at any time.
- 4. Exclude subjects meeting the Anti-Hypertensive Medication Escape Criteria (OSBP >180 mmHg or safety reasons).
- 5. Exclude subjects who did not receive the treatment they were randomized to.

Office and ambulatory blood pressure outcomes out to 3 months will be presented for this population.

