## D SUBJECT SELECTION

### D.1 Inclusion criteria

1. Individual is  $\geq 20$  and  $\leq 80$  years old at time of enrollment (consent).
2. Individual has an office systolic blood pressure (SBP)  $\geq 150$  mmHg and  $<180$  mmHg, and a diastolic blood pressure (DBP)  $\geq 90$  mmHg at Screening Visit 2, according to guidelines in Appendix L.7.
3. Individual has a 24-hour Ambulatory Blood Pressure Monitoring (ABPM) average SBP  $\geq 140$  mmHg and  $<170$  mmHg at Screening Visit 2 according to guidelines in Appendix L.7: ABPM is considered valid if the number of successful daytime readings captured is  $\geq 21$  and the number of successful nighttime readings captured is  $\geq 12$ .

4. Individual agrees to have all study procedures performed, and is competent and willing to provide written, informed consent to participate in this clinical study.
5. Individual is willing to discontinue current antihypertensive medications at Screening Visit 1 through the three month post-procedure visit.

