## D.2 Exclusion criteria

1. Individual has one or more of the following conditions: stable or unstable angina within 3 months of enrollment, myocardial infarction within 3 months of enrollment; heart failure, cerebrovascular accident or transient ischemic attack, or atrial fibrillation at any time. Patients are permitted to take aspirin or clopidogrel for cardiovascular risk reduction. Patients who received catheter or surgical treatment for Atrial Fibrillation and are in sinus rhythm are not excluded.
2. Individual has undergone prior renal denervation.
3. Individual has renal artery anatomy that is ineligible for treatment including:
  - a. Main renal artery for each kidney less than 3mm or greater than 8mm
  - b. Lacks a main renal arterial vessel (greater than 3mm and less than 8mm in diameter) for each kidney that does not allow 4 simultaneous quadrantic (4SQ) radio frequency ablations in the main renal artery or equivalent (defined as 4SQ ablations in all branch vessels greater than 3mm and less than 8mm)
4. Presence of FMD (defined as visible beading of the artery on angiography)
5. Has >50% stenosis in any treatable vessel
6. Has a renal artery stent placed <3 months prior to the denervation procedure
7. Presence of an aneurysm defined as any localized increase in the diameter of the vessel
8. Treatment area within 5mm of a segment in the renal artery which contains any of the following:
  - a. Atheroma,
  - b. Calcification, or
  - c. Renal artery stent
9. Individual has an estimated glomerular filtration rate (eGFR) of <45 mL/min/1.73m^2, using the 4 variable MDRD calculation (in mL/min per 1.73 m^2 = 175 x SerumCr-1.154 x age-0.203 x 1.212 (if patient is black) x 0.742 (if female)). (NOTE: an eGFR calculation specific to Japanese patients will be used for subjects enrolled in Japan)
10. Individual has documented type 1 diabetes mellitus or poorly-controlled type 2 diabetes mellitus with glycosylated hemoglobin greater than 8.0%.
11. Individual is taking SGLT2 inhibitors or GLP-1 agonists that have been prescribed < 90 days from Screening Visit 1 or who does not plan to remain on these drugs for the duration of the trial
12. Individual has had ≥1 episode(s) of orthostatic hypotension not related to medication changes within the past year or reduction of SBP of ≥20 mmHg or DBP of ≥10 mmHg within 3 minutes of standing coupled with symptoms during the screening process (at SV2).

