  - **Renin and Aldosterone (blood):** Samples should be collected in the morning after the patient has been out of bed for  $\geq 2$  hours and after resting quietly sitting for a minimum of 5 minutes but preferably 30 minutes. The time of day and subject's position (standing, sitting, or lying down) when the blood sample is collected should be documented and the same time of day ( $\pm 2$  hours) and subject position should be used for collection of blood samples for determination of renin and aldosterone at later time points in the study.
  - **Drug testing (urine/blood)** to ensure medications are no longer present in the subject's system. A urine sample will be collected, preferably using the subject's first morning urine. A blood sample will be collected at the time of the visit.
- f. **24-hour Ambulatory Blood Pressure Monitoring** will be applied at the conclusion of Screening Visit 2 to confirm subject's baseline blood pressure. This value will be utilized as the baseline value for calculating change in 24-hour ABPM at various time points post-procedure. Subjects with a 24-hour systolic ABPM of  $< 140$  or  $\geq 170$  mmHg after completion of the screening visit will be exited from the study. Subjects with a 24-hr systolic ABPM of  $\geq 140$  and  $< 170$  mmHg are eligible to continue to the randomization (procedure or control) visit. A single repeat measurement is allowed in case of the following: 1.) a technical issue with the blood pressure monitor or failure to follow ABPM instructions, or 2.) if a valid number of readings is not obtained, or 3.) if the 24-hr systolic ABPM measured

135 - <140 mmHg or 170-175 mmHg. ABPM must be conducted according to the guidelines in Appendix L.7. If ABPM is repeated office blood pressure and drug testing must be repeated on day the ABPM is applied.

- g. **Adverse Event Reviews** will be completed to document adverse events that occur after enrollment.
- h. **Baseline Renal Imaging** Submit a baseline Duplex Ultrasound, CT, or MRA if obtained per standard of care prior to procedure within one year from the date of the screening visit 1 and upload via Intelemage or send via courier.

Subjects determined to not be eligible for randomization will be exited from the study, as described in the Subject Exit from Study section of this Clinical Investigation Plan.

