- b) **SF-36:** The 36-Item Short Form Survey (SF-36) will be administered at the 3, 6, 12, 24 and 36 month post-procedure visits to measure health outcomes.
- c) **Clinical Assessment** will be conducted at all post-procedure follow-up visits to evaluate the subject's current medical condition. An individual experienced in performing histories and physical exams is required to assess subjects for safety assessment during the period of time that study subjects are not on antihypertensive medications.
- d) **Office Blood Pressure** measurements will be obtained in accordance with Appendix L.7 at all post-procedure follow-up visits.
- e) **Laboratory Tests:**
  - **Basic metabolic panel Chem-7 (blood):** serum-creatinine, sodium, potassium, blood urea nitrogen (BUN), bicarbonate, chloride and glucose. Bicarbonate will not be measured for subjects enrolled in Japan and Europe.
  - **eGFR** will be calculated from the serum-creatinine in the Chem-7 panel for eligibility criteria by using the 4 variable Modification of Diet in Renal Disease (MDRD) Formula or the local Japanese criteria for subjects enrolled in Japan.
  - **Renin and Aldosterone testing (blood; 3 month follow-up only)** Samples should be collected in the morning after the patient has been out of bed for  $\geq 2$  hours and after resting quietly after a minimum of 5 minutes but preferably 30 minutes. The time of day and subject's position (standing, sitting, or lying down) before the blood sample is collected should be documented and the same time of day ( $\pm 2$  hours) and subject position should be used for collection of blood samples for determination of renin and aldosterone at later time points in the study.
  - **Drug testing (urine/blood)** to ensure no medications are present in the subject's system at 3 months follow-up and to ensure that prescribed medications are in the subject's system at 6, 12, 24, and 36 months. A

urine sample will be collected, preferably using the subject's first morning urine. A blood sample will be collected at the time of the visit.

- f) **Initiate Medication Re-Introduction for Subjects with Systolic OBP  $\geq$  140 mmHg at 3M follow-up visit.** Starting at 3 month follow-up after clinical assessment and a valid ABPM are completed.
- g) **Medication & Adverse Event Reviews** will be completed at each follow-up visit to assess any changes in medication usage or medical condition:

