#### H.1.1 Analysis Sets

- a. Intent-to-Treat (ITT): All randomized subjects, analyzed according to their randomized treatment. Subjects who meet the antihypertensive medication escape criteria (OSBP>180 or safety reasons) will be analyzed using Last Observation Carried Forward (LOCF) for their blood pressure measurements.
- b. Modified Intent-to-Treat : All randomized subjects, analyzed according to their randomized treatment. Subjects who meet the antihypertensive medication escape criteria (OSBP>180 or safety reasons) will be excluded from this population.
- c. Per-Protocol (PP): All randomized subjects, meeting the following criteria:
  1. Subjects showing medication compliance in blood and/or urine (via drug testing data) at SV2 and 3M

2. Exclude subjects with protocol deviation code 101 (consent not obtained)
  3. Exclude subjects who do not meet the following Inclusion/Exclusion criteria
    - Inclusion: Individual has an office systolic blood pressure (SBP)  $\geq$  150 mm Hg and  $<$ 180 mm Hg and an office DBP  $\geq$  90 mm Hg measured at Screening Visit 2, according to the guidelines in Appendix L7.
    - Inclusion: Individual has a 24-hour ABPM average SBP  $\geq$ 140 and  $<$  170 mm Hg measured at Screening Visit 2, according to guidelines in Appendix L7.
    - Exclusion: Individual has undergone prior renal denervation
    - Exclusion: Individual has renal artery anatomy that is ineligible for treatment
    - Exclusion: Individual has one or more of the following conditions: stable or unstable angina within 3 months of enrollment, myocardial infarction within 3 months of enrollment; heart failure cerebrovascular accident or transient ischemic attack or atrial fibrillation at any time.
  4. Exclude subjects meeting the antihypertensive medication escape criteria (OSBP $>$ 180 or safety reasons).
  5. Exclude subjects who did not receive the treatment they were randomized to.
- d. As Treated Population: All randomized subjects, analyzed according to the actual treatment received. Subjects randomized to RDN who do not get treated will be analyzed in the control arm. Subjects who meet the anti-hypertensive medication escape criteria will be analyzed using Last Observation Carried Forward (LOCF) for their blood pressure measurements out to 3 months.

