## 9.11. Subgroup Analyses

Analysis will be carried out for the following subgroups to assess consistency of results.

- Gender
- Age at baseline <65 vs. ≥ 65 (years)

- BMI by tertiles (kg/m^2)
- Type 2 diabetics vs. non-diabetics
- Current smokers vs. non-smokers
- Baseline eGFR < 60 vs. ≥ 60 (mL/min/1.73 m²)

- Obstructive sleep apnea yes vs. no
- US vs. OUS Subjects
- US African American vs. US Non African American subjects
- European vs. Japanese vs. Australian subjects
- Baseline ambulatory SBP by tertiles and medians (mmHg)

- Baseline office SBP by tertiles and medians (mmHg)
- Baseline ambulatory heart rate by tertiles and medians (bpm)
- Baseline office heart rate by tertiles and medians (bpm)
- 24-Hour Pulse Pressure <60 vs. >= 60 mmHg (mmHg)
- Orthostatic Hypertension at baseline
- Orthostatic Tachycardia at baseline
- Plasma Renin Activity at baseline <0.65 vs. ≥0.65 (ng/mL/h)

- Aldosterone Renin Ratio at baseline by tertiles
- Aldosterone at baseline by tertiles (ng/dL)
- Tertile analysis by total number of ablations performed
- Tertile analysis by total number of ablations performed in branch vessels
- Tertile analysis by total number of ablations performed in main renal artery vessels
- Tertile analysis by total number of 45 second ablations performed
- Medication adherent vs. non-adherent subjects at screening visit 2 (SV2) and 3 months (from urine and serum tests)

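### The per-protocol set omits the treated-AF exception in exclusion 1, and its drug-test rule does not say whether a subject with drug in one sample stays in

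*SAP*

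**What the plan says.** **Drug testing.** SAP 9.1.3.3 item 1 admits "Subjects showing medication compliance in blood and/or urine (via drug testing data) at screening visit 2 (SV2) and 3-months". Protocol H.1.1 c.1 has the same rule: "Subjects showing medication compliance in blood and/or urine (via drug testing data) at SV2 and 3M". Neither document defines compliance, or says what happens when the two samples disagree or one is missing. The protocol collects both urine and blood at each visit. Under F.5 (Screening Visit 2) the purpose is "to ensure medications are no longer present in the subject's system"; under F.7 it is "to ensure no medications are present in the subject's system at 3 months follow-up". The adherence subgroup in SAP 9.11 and Protocol H.9 is worded differently: "Medication adherent vs. non-adherent subjects at screening visit 2 (SV2) and 3 months (from urine and serum tests".

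**Atrial fibrillation.** Item 3 of the per-protocol list, in both documents, removes subjects who fail certain named eligibility criteria. One bullet restates exclusion 1, ending "heart failure cerebrovascular accident or transient ischemic attack or atrial fibrillation at any time". Exclusion 1 itself, in the synopsis and in D.2, carries a further sentence: "Patients who received catheter or surgical treatment for Atrial Fibrillation and are in sinus rhythm are not excluded". The per-protocol list does not repeat it.

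**Role of the set.** ITT is the primary population for both powered efficacy endpoints. Per-protocol is one of three secondary populations (SAP 9.9.4 and 9.9.5.1), and the other secondary efficacy endpoints are also shown for it (SAP 9.9.8).

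**The concern.** A per-protocol set in an off-medication trial should hold subjects who met the entry criteria and were free of antihypertensive drug when their pressure was measured. The two items fall short of that in opposite directions. The AF bullet can take out a subject who broke no rule. The drug-test item can leave in a subject whose urine or blood showed an antihypertensive.

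The word *compliance* adds to the difficulty because it changes meaning during the trial. At SV2 and 3 months the test is looking for absence of drug; from 6 months on, F.7 uses it to confirm that prescribed drugs are present. Detection in either sample can establish that a drug was taken, but absence in one sample does not cancel detection in the other.

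The per-protocol result may be read as confirming that the effect holds in eligible, drug-free subjects. If membership turns on a choice that the SAP does not state, the reader cannot tell whether the set supports that reading.

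**Working it through.** The documents give no figure to reproduce: no per-protocol set size, no drug-positive rate and no count of treated-AF subjects. The check is a comparison of texts plus a count of result patterns.

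**1. AF bullet against exclusion 1.**
- D.2 item 1 and the synopsis: AF at any time excludes, except after catheter or surgical treatment with sinus rhythm.
- SAP 9.1.3.3 item 3 and Protocol H.1.1 c.3: AF at any time excludes, with no exception.
- A subject with ablated AF in sinus rhythm passes the first and fails the second. The protocol therefore disagrees with itself as well as with the SAP.
- The change history records that the exception entered exclusion 1 at protocol version 9.0. Only subjects enrolled under a version carrying it could be validly enrolled and then removed. The documents do not say how many there were; it could be none.

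**2. Drug-test item: what the wording permits.** Each sample is negative or positive, so one visit with both samples has 2 × 2 = 4 patterns.
- Either sample negative is enough: keeps 4 − 1 = 3 patterns, including the 2 discordant ones.
- Both samples must be negative: keeps 1 pattern.
- Over SV2 and 3 months: 4² = 16 patterns in all; the first rule keeps 3² = 9, the second 1² = 1. The other 9 − 1 = 8 depend on how the item is read.

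These are counts of patterns, not proportions of subjects; the patterns are not equally likely. A third reading accepts one sample when the other was not obtained. The item decides among none of the three.

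**3. Is an eligibility rule broken by item 1?** Inclusion 5 reads "Individual is willing to discontinue current antihypertensive medications at Screening Visit 1 through the three month post-procedure visit". It concerns willingness, and no criterion in D.1 or D.2 turns on a drug-test result. The tension is with the stated purpose of the tests in F.5 and F.7.

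**4. Possible size, on assumptions only.** If discordant subjects are kept, the 3-month between-group difference moves by roughly (discordant share in sham − share in RDN) × drug effect. The shares and the effect below are assumed.
- Equal shares: 0 × effect = 0.
- Sham 10%, RDN 5%, effect 5 to 10 mmHg: 0.05 × 5 = 0.25 to 0.05 × 10 = 0.50 mmHg toward zero. Against the planned −4.0 mmHg (SAP Table 3) that is 0.25/4.0 = 6.25% to 0.50/4.0 = 12.5%.
- Shares reversed: the same amounts, away from zero.
- Drug present at SV2 lowers the baseline and pushes the change the other way.

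The illustration therefore runs from 0.50 mmHg in one direction through zero to 0.50 mmHg in the other. It shows scale only; neither size nor sign follows from the documents.

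**The case against.** The case for leaving the text alone has five parts.

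- *And/or is not or.* The wording also supports requiring both samples, or accepting one when the other is missing. This stands: a reader might infer that the plan keeps drug-positive subjects, but the text only allows it.
- *The detail may exist elsewhere.* The SAP version history says that the algorithms for selecting drug-testing values were moved to the study table specifications, which were not available for this review. This also stands, and it means the rule actually applied is unknown. It does not remove the need for the population definition to be clear in the SAP.
- *The AF bullet is shorthand for the whole of exclusion 1.* Possible, but neither document says so, and the bullet reproduces the rest of the excluding conditions while leaving out the exception.
- *The consequence is small.* ITT is primary, per-protocol carries no success criterion, and the SAP also plans modified-ITT and as-treated analyses and an assessment of how adherence affects blood pressure change (9.9.9). Subjects meeting the escape criteria are already removed by item 4. All of this stands and limits the point.
- *It is late.* Protocol B.1.2 reports that enrollment stopped for efficacy in February 2020 and that 3-month results were presented in March 2020. Changing an analysis set now is more than an edit. This stands and shapes the fix.

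**Conclusion.** The AF half holds on the text: as written, item 3 removes subjects whom exclusion 1 expressly admits. The drug-test half holds as an undefined rule: item 1 permits, without requiring, retention of a subject with an antihypertensive detected in one sample, against the purpose stated for the tests.

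Two stronger readings are not supported. The per-protocol set does not demonstrably contradict the off-drug rule, because a both-samples reading is open and the operating algorithm is not in the documents. The drug-test item contradicts no eligibility criterion, because none depends on a test result.

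The effect is confined to the secondary per-protocol analyses and, so far as it relies on the same undefined notion of compliance, the adherence subgroup. The primary ITT analyses are untouched. The size cannot be derived; the 0.25 to 0.50 mmHg illustration depends on assumed unequal discordance and vanishes when the arms are alike.

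**What to change.** 1. In SAP 9.1.3.3 item 3 and Protocol H.1.1 c.3, add the exclusion 1 sentence on treated AF in sinus rhythm.
2. In SAP 9.1.3.3 item 1 and Protocol H.1.1 c.1, define compliance as no antihypertensive detected in either the blood or the urine sample paired with the ABPM used in the analysis, at SV2 and again at 3 months. The pairing matters: F.5 and F.7 require drug testing and office pressure to be repeated on the day a repeat ABPM is applied, so a visit can have two sets of samples. A rule covering every sample at the visit would remove a subject who was clean at the recording actually analysed.
3. State how a subject with one sample missing, or both, is classified, and report the number of such subjects and of discordant results by arm.
4. Use the same definition for the adherence subgroup in SAP 9.11 and Protocol H.9, and keep the table specifications consistent with it.
5. State which rule was used in any per-protocol analysis already run. Label a re-run under the new definition as a change made after results were known, and justify it in the final report, as the opening of Protocol section H requires for deviations.

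The cost is text in four places and, where needed, a re-run of the per-protocol and subgroup tables. The per-protocol set may shrink slightly under item 1, while item 3 may restore a few subjects. No new data are needed.
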